## 9. ETHICAL CONSIDERATIONS

### 9.1 GENERAL CONSIDERATIONS

This study will be conducted in conformity with the requirements of the “Declaration of Helsinki” adopted by the 18th World Medical Association General Assembly held in Helsinki, Finland, June 1964 and relevant revisions. The Good Clinical Practice (GCP) issued by the working group on the Efficacy of Medicinal Substances of the European Union (1990) (CPMP/ICH/135/95) and applicable regulatory requirements and laws on the country where the Trial is taking place.

According to Directive 95/46 of the European parliament and 2001/20 /EC by which the requirements to perform a clinical trial are established, the information obtained in the course of the clinical trial, will only be able to be used by the clinical trial sponsor to evaluate the results according to the mentioned regulation.

### 9.2 WRITTEN INFORMED CONSENT

Is the obligation of de Investigator to obtain a written informed consent of the subjects (according to the requirements according the European directive of Clinical Trials), before including a patient in the trial, or when needed, before assessing the eligibility of subject for the study.

Each subject or her/his legal representative will be required in the terms established in European Directive for clinical trials, granting free written informed consent after receiving oral and written information about the trial objectives, procedures to follow, the possible benefits, drawbacks and expected risks, possible therapeutic alternatives as well as their rights and responsibilities. The patient or his representative must be informed that their participation is voluntary and they can withdraw at any time without incurring any consequences. It should also be informed that the Sponsor, their representatives and competent authorities will have access to clinical data.

The Investigator will be responsible for providing each subject or her/his representative a Patient Information Sheet and Informed Consent Form approved by the relevant ethics committee.

If the patient agrees to participate in the study, itself or her/his legal representative must sign the consent form. The investigator must also sign and date this form, thus indicating that it has obtained informed consent and that the patient has had the opportunity to ask questions and these have been properly answered.

The patient or her/his representative will receive a copy of the Patient Information Sheet and the informed consent form signed.

The Investigator will archive in the patient records of each subject the original informed consent forms signed and dated. No patient may participate in the study until signing the informed consent.

### 9.3 DATA CONFIDENTIALITY

The confidentiality of the data of each patient will be respected at all times. In order to warrant the confidentiality of study data according to [Regulation \(EU\) No. 2016/679 General Data Protection \(RGPD\)](#), and [Organic Law 3/2018, of December 5, Protection of Personal Data and guarantee of digital rights](#) ~~Directive 95/46 of the European parliament and 2001/20/EG~~, personal and clinical data can only be accessed by the Sponsor of the study or its designated staff, for monitoring/auditing purposes, the investigator and team of collaborators, the Ethics Committee of the investigational site, or the one overseeing the centre, and pertinent Health Authorities.

Study subjects will be identified by a unique code consisting in site number (two digits) and

consecutive number according to chronological order of recruitment (two digits).

The investigator will inform the study subjects that data obtained in this trial will be stored and analysed by computer and that the European regulations on the management of computerized data will be followed. Data protection is described in the patient information sheet in writing.

The Investigator accepts that the Sponsor has the right to use the results of the clinical trial, including CRF forms or copies thereof. To allow the use of information obtained in the clinical trial, the investigator understands that he is obligated to provide full test results and all information developed during the study to the Sponsor.

Version 3.2: September 16th, 2020

#### **9.4 CLINICAL TRIAL INSURANCE**

The trial will have an insurance policy that will cover all possible damages that patients may suffer as a result of product tested, according to local applicable laws in the country where the study is conducted.

#### **9.5 EC SUBMISSION**

This protocol and all required documentation will be submitted for evaluation to the relevant Ethics Committee following the procedure established in current European regulation and the instructions of health authorities in the countries where the trial takes place.

The study will not begin until the EC positive vote and Competent Authority be available for the study, and other local requirements established by current legislation are met. The Sponsor will provide the Investigator with a copy of the relevant documents.

The Ethics Committee and the relevant health authorities will be informed of all changes to the protocol that may affect the safety of the subjects or the conduct of the trial and the severe and unexpected reactions and other information that may alter the design of the study or imply a risk for the patients. The corresponding approvals/authorizations will be obtained In the case of substantial amendments to the protocol, according to what is established in European Directive and guidelines.

## **10. PRACTICAL CONSIDERATIONS**

### **10.1 RESPONSIBILITIES ACCORDING TO GCPs**

The Sponsor, monitor and investigators will comply the responsibilities established in the GCPs.

#### **10.1.1 Investigator**

- a) To agree and sign the study protocol.
- b) To know in depth all study drugs characteristics.
- c) To obtain informed consent of subjects before inclusion in the trial.
- d) To ensure that adequate medical care is provided to a subject for any adverse events, including clinically significant laboratory valued, related to the trial.
- e) To collect, register and notify data in a correct way.
- f) To notify immediately to the sponsor all SAE and unexpected adverse events.
- g) To take responsibility that all people involved in the trial will respect the confidentiality of any information about the study subjects.
- h) To keep the Ethics Committee regularly informed on the facts of the study.
- i) To take co-responsibility on the elaboration of the final study report, providing his/her agreement and signature.

#### **10.1.2 Sponsor**

- a) The sponsor is responsible for implementing and maintaining quality assurance and quality control systems with written SOPs to ensure that trials are conducted and data are generated, documented (recorded), and reported in compliance with the protocol, GCP, and the applicable regulatory requirement(s).
- b) To sign with the respective investigator the protocol and any amendment to the protocol.
- c) To select the most suitable investigator based on the investigator's qualifications and availability of resources, and to assure the investigator's agreement to conduct the trial as specified in the protocol.
- d) To provide all available basic and clinical information on the investigational medicinal product and maintain it updated throughout the duration of the trial.
- e) To request the report by the Clinical Research Ethics Committee and authorization by the Spanish Agency for Medicines and Medical Devices and to submit notification or application, as appropriate and without prejudice to notification of autonomous communities, in the event of any amendment or violation of the protocol, discontinuation of the trial and reasons for discontinuation.
- f) To provide the investigational medicinal products at no cost and to ensure that they have been prepared according to good manufacturing practice and are suitably packaged and labeled. The sponsor is also responsible for the storage of investigational products and for keeping records of their manufacture and quality control, to keep records of the investigational medicinal products supplied and to ensure that the site where the trial is conducted establishes a procedure for correct handling, storage and use of investigational medicinal products delivered.

In exceptional cases, other means of supply may be agreed with the site.

- g) To appoint the monitor who shall supervise the performance of the trial.
- h) To notify health authorities and Clinical Research Ethics Committees involved in the trial of any unexpected or serious adverse events in accordance with the procedures established in European and local directive.
- i) To inform promptly the investigator and Clinical Research Ethics Committee of any new relevant information that becomes available during the trial.
- j) To provide compensation for the subjects in the event of trial-related injury or death. To provide legal and financial cover for the investigator, except for claims resulting from malpractice or negligence by the investigator.
- k) To agree with the investigator on the allocation of responsibilities for data processing, preparation of reports, and publication of results. In any case, the sponsor is responsible for preparing final or partial reports of the trial and submitting them to the appropriate authorities.
- l) The sponsor shall provide a contact point, where the trial subjects may obtain further information about the trial, which may be delegated on the investigator.

### **10.1.3 Monitor**

Monitoring task are delegated by the Sponsor to MFAR.

- a) To work according to sponsor standard operating procedures, visit the investigator before, during and after the trial to control adherence to the protocol and assure that all data are correctly and completely recorded and reported, and that informed consent is obtained from all subjects prior to their enrolment in the trial.
- b) To ensure that both the investigators and the sites where the trial is to be conducted are adequate for this purpose for the duration of the trial.
- c) To ensure that both the principal investigator and all staff assisting the investigator are adequately informed and to ensure communications between the investigator and sponsor promptly at all times.
- d) To check that the investigator complies with the protocol and all approved amendments.
- e) To check that the storage, dispensing, return and documentation of the supply of investigational medicinal products are safe and appropriate.
- f) To submit written reports to the sponsor after each monitoring visit and after all relevant contacts with the investigator.

## **10.2 PROTOCOL AMENDMENTS AND PROTOCOL DEVIATIONS**

After the protocol is reviewed and signed, neither the investigator nor the Sponsor can make changes or alterations without the written consent of both.

If it is needed to perform any modification or alteration to the protocol one it has been signed, this modification should be discussed and agreed between the principal investigator and the sponsor, and signed by both parties. The amendments to the protocol should form an integral part of the original protocol. The ethics committee must be informed of all amendments to the protocol that may affect the safety of the subjects or the conduct of the trial. In case of relevant amendments the approval of the amendment should be obtained, in accordance of European and Local regulations, before implementing such modifications.

### 10.3 MONITORING

A team of monitors appointed by the Sponsor will monitor the study regularly to ensure the safeguarding of rights and welfare of patients, the protocol is followed accordingly, the applicable standards and ethical requirements are met, all necessary documentation is available in Sites and the data is collected accurately.

The Investigator must grant access to the monitor to subjects medical records, study records, CRF, signed original informed consent forms and all source data documents.

Any deficiency observed during monitoring visits will be discussed with the investigator, reaching agreement on the corrective measures to be implemented.

### 10.4 DATA MANAGEMENT

All data (personal, clinical, economic, derived from biologic material) obtained from patients will be handled according to the [Regulation \(EU\) No. 2016/679 General Data Protection \(RGPD\), and Organic Law 3/2018, of December 5, Protection of Personal Data and guarantee of digital rights](#) ~~Directive 95/46/EC of the European Parliament and of the Council of 24 October 1995 on the protection of individuals with regard to the processing of personal data~~. According to such legislation, patients will be able to exert their rights to access, modification, opposition and cancellation of their data, for which the clinical trial physician must be addressed. The content of the CRFs, as well as the documents generated during the study will be considered strictly confidential and not revealed to third parties.

The investigator should keep detailed records of all subjects involved in the trial.

The investigator should collect and record data from the study in the medical records of each subject and then, transfer the information to the CRF provided by the Sponsor. All data must be completely recorded, without delay, accurately and intelligible in the CRF.

The investigator should date and sign each of the CRF in the specific field of the eCRF.

The researcher should keep all the original documentation (lab results, treatment sheets, signed Informed Consent, etc.).

Data recorded in the CRF will be reviewed and analysed; data from the database will also be reviewed to detect inconsistencies. Doubtful, inconsistent or incomplete data will be queried to the investigator in written and correction will be tracked in the audit trail of the CRF.

Correction procedures of computerized data will be applied.

### 10.5 STUDY DOCUMENTATION ARCHIVING

It is the responsibility of the investigator to ensure the maintenance of trial file in the study site. For this trial the file will contain, but not be limited to, the following documentation:

1. Protocol Study, current and previous version, revision and/or amendments (when applicable);
2. Patient information sheet and consent form, revision and/or amendments (when applicable);
3. Investigator commitment;
4. Contract for clinical research;
5. Investigator and sub-investigators CV;
6. EC Positive Vote for the trial and amendments (when applicable) and other relevant communications with the EC;

7. CA approval for the trial and amendments (when applicable) and other relevant communications with the CA;
8. Correspondence between Investigators, EC and Sponsor related to this trial;
9. Annual reports and safety reports;
10. Normal laboratory ranges, in which the determinations required in this trial be detailed. Quality certification for this laboratories;
11. IMP documentation (accountability forms, conservation, etc.);
12. Updated Clinical Trial Staff Signature list and delegation log;
13. Subject identification list, for patients enrolled in the trial.

The investigator should file the subject identification list and all signed informed consent for at least 15 years after completion of the trial. Any original information related to the study that allow the verification of the criteria for inclusion and exclusion, including medical records, a copy of all case report forms and documents for use of investigational product should be stored for the maximum time allowed by the Site.

#### **10.6 QUALITY CONTROL AND QUALITY ASSURANCE**

The study will be overseen by MFAR, SL monitors. The study monitor will contact investigators periodically. In these contacts the progress of the study will be discussed with the investigator and will be checked that CRFs are filled out in full and consistently manner. Study Monitor (and, when requested, a representative from the sponsor) will also check the informed consent forms.

With a proper supervision and guarantee of confidentiality, the investigator will allow to the representative of the sponsor or to the study monitor to compare the data entered in the CRF with the original data in the study site (source documents), and to observe the study procedures in order to verify the study protocol compliance.

#### **10.7 INSPECTION AND AUDITING**

Audits of quality assurance may be performed at anytime during the trial or after completion. Also, the study may be inspected by the relevant authorities on the terms established in the European and local regulations.

Upon request of the monitor, auditor, ethics committee or regulatory authorities, the investigator should provide direct access to all documents related to the clinical trial.

#### **10.8 STUDY EARLY TERMINATION**

The Sponsor may, at any time, suspend the participation of an investigator in the study. In the event that the participation of an Investigator on a study be suspended, the Sponsor will inform promptly and in writing to the EC and CA about the reason or reasons for the suspension.

The study early termination may be due, among others, the following reasons:

- New information available that justify that the continuation of the study is not feasible.
- Unsatisfactory recruitment in terms of quantity or quality.
- Data collection inaccurate or incomplete.
- Protocol non compliance.

## **10.9 FINANCIAL ASPECTS OF THE TRIAL**

Financial aspect of the trial will be submitted to EC for evaluation at the protocol submission.

## **10.10 PUBLICATION POLICY**

The Sponsor and Investigators are committed to publish the results of this study. All publications and presentations proposed by the Investigators or his/her staff and associates resulting from or related to the study, should be submitted to the Sponsor for timely review before being submitted for publication or presentation.

In publications the signing authors will be sorted by number of patients included, from highest to lowest accrual.

If the proposed publication or presentation contains patentable material, which, in the Sponsor opinion, guarantees the protection of intellectual property, it may delay any publication or presentation for a reasonable period of time in order to achieve such protection.

## **ANNEXES**

- I. List of participating Sites
- II. Study Patient Information Sheet and Consent Form
- III. Molecular Sub-study Patient Information Sheet and Consent Form
- IV. ECOG Performance Status
- V. NCI CTCAE V4.0
- VI. SmPC of Ibrutinib
- VII. Recommendations for initial evaluation, staging, and response assessment of Hodgkin and non-Hodgkin lymphoma: the Lugano classification (13)

## **APPENDIX I. Participating Sites**

A list of participating sites will be available as an independent document.

## **APPENDIX II. Patient Information Sheet and Informed Consent Form**

The current Patient Information and Study Informed Consent sheets are available as a separate document.

Version 3.2: September 16th, 2020

**APPENDIX III. Sheet Patient Information and Informed Consent molecular substudy**

The current Patient Information and Study Informed Consent sheets are available as a separate document.

Version 3.2: September 16th, 2020

**APPENDIX IV. ECOG Performance Status**

0	Fully active, able to carry on all pre-disease performance without restriction.
1	Restricted in physically strenuous activity but ambulatory and able to carry out work of a light or sedentary nature, e.g., light housework, office work.
2	Ambulatory and capable of all selfcare but unable to carry out any work activities; up and about more than 50% of waking hours.
3	Capable of only limited selfcare; confined to bed or chair more than 50% of waking hours.
4	Completely disabled; cannot carry on any selfcare; totally confined to bed or chair.
5	Death.

## **APPENDIX V. NCI CTCAE V4.0**

Version 4.0 of CTC is available at:

[https://evs.nci.nih.gov/ftp1/CTCAE/CTCAE\\_4.03/CTCAE\\_4.03\\_2010-06-14\\_QuickReference\\_8.5x11.pdf](https://evs.nci.nih.gov/ftp1/CTCAE/CTCAE_4.03/CTCAE_4.03_2010-06-14_QuickReference_8.5x11.pdf)

A paper copy is included in the investigator's site file.

## **APPENDIX VI. Ibrutinib SmPC**

The current Ibrutinib SmPC is available as a separate document.

Version 3.2: September 16th, 2020

**ANNEX VII. Revised Criteria for Response Assessment**

Lugano Criteria for Response Assessment for Non-Hodgkin Lymphoma (13)

Response and Site	PET-CT–Based Response	CT–Based Response
Complete	Complete metabolic response	Complete radiologic response
Lymph nodes and extralymphatic sites	Score 1, 2, or 3 with or without a residual mass on 5PS†  It is recognized that in Waldeyer's ring or extranodal sites with high physiologic uptake or with activation within spleen or marrow (eg, with chemotherapy or myeloid colony-stimulating factors), uptake may be greater than normal mediastinum and/or liver. In this circumstance, complete metabolic response may be inferred if uptake at sites of initial involvement is no greater than surrounding normal tissue even if the tissue has high physiologic uptake	Target ganglia / ganglion masses should decrease by $\leq 1.5$ cm in LDi No extralymphatic sites of disease
Non Measured lesion	Not applicable	Absent
Organ enlargement	Not applicable	Back to normal
New lesions	None	None
Bone marrow	No evidence of FDG-avid disease in marrow	Normal by morphology; if indeterminate, IHC negative
Partial	Partial metabolic response	Partial radiologic response
Lymph nodes and extralymphatic sites	Score 4 or 5† with reduced uptake compared with baseline and residual mass(es) of any size At interim, these findings suggest responding disease At end of treatment, these findings	$\geq 50\%$ decrease in SPD of up to 6 measurable target nodes and extranodal sites. When a lesion is too small to measure on CT, assign 5mm $\times$ 5mm as the default value.

	indicate residual disease	When no longer visible, 0 × 0 mm. For a node > 5mm × 5mm, but smaller than normal, use the actual measurement for the calculation.
Non Measured lesions	Not applicable	Absent / normal, regress, but no increase
Organ enlargement	Not applicable	None
New lesions	None	Not applicable
Bone marrow	Residual uptake higher than uptake in normal marrow but reduced compared with baseline (diffuse uptake compatible with reactive changes from chemotherapy allowed). If there are persistent focal changes in the marrow in the context of a nodal response, consideration should be given to further evaluation with MRI or biopsy or an interval scan	Not applicable
No response or stable disease	No metabolic response	Stable disease
Target nodes/nodal masses, extranodal lesions	Score 4 or 5 with no significant change in FDG uptake from baseline at interim or end of treatment	<50% decrease from baseline in SPD of up to 6 dominant measurable nodes and extranodal sites; criteria for disease progression are not met
Non Measured lesions	Not applicable	No increase consistent with progression
Organ enlargement	Not applicable	No increase consistent with progression
New lesions	None	None
Bone marrow	No change from baseline	Not applicable
Progressive disease	Progressive metabolic disease	Progressive disease requires at least 1 of the following
Individual target	Score 4 or 5 with an increase in	A single node / lesion must be

nodes/nodal masses	intensity of uptake from baseline and/or	abnormal with: LDi > 1.5 cm and ≥50% increase from PPD nadir and An increase in LDi or SDi from nadir 0.5 cm for lesions ≤ 2 cm 1.0 cm for lesions > 2 cm In the setting of splenomegaly, splenic length should increase by > 50% of the extent of its previous increase beyond the baseline (eg, a 15 cm spleen should increase to > 16 cm). If there is no previous splenomegaly, it should increase at least 2 cm from the initial value New or recurrent splenomegaly
Extranodal lesions	New FDG-avid foci consistent with lymphoma at interim or end-of-treatment assessment	
Non Measured lesions	None	New progression or clear progression of unmeasured pre-existing lesions
New lesions	New FDG-avid foci consistent with lymphoma rather than another etiology (eg, infection, inflammation). If uncertain regarding etiology of new lesions, biopsy or interval scan may be considered	Regrowth of previously resolved injuries. A new node > 1.5 cm on any axis. A new extranodal site > 1.0 cm in any axis; if it is < 1.0 cm in any axis, its presence must be unequivocal and attributable to lymphoma Assessable disease of any size unequivocally attributable to lymphoma
Bone marrow	New or recurrent FDG-avid foci	New or recurrent alteration

Abbreviations: 5PS, 5-point scale; CT, computed tomography; FDG, fluorodeoxyglucose; IHC, immunohistochemistry; LDi, longest transverse diameter of a lesion; MRI, magnetic resonance imaging; PET, positron emission tomography; PPD, cross product of LDi and perpendicular diameter; SDi, shortest axis perpendicular to LDi; SPD, sum of the product of the perpendicular diameters for multiple lesions.

\* A score of 3 in many patients indicates a good prognosis with standard treatment, especially if performed at the time of an interim examination. However, in trials involving PET investigating de-escalation, it may be preferable to consider a score of 3 as an inadequate response (to avoid

insufficient treatment). Measured dominant lesions: Up to six of the largest dominant nodes, lymph node masses, and extranodal lesions selected to be clearly measurable in two diameters. The nodes should preferably be from disparate regions of the body and should include, where applicable, mediastinal and retroperitoneal areas. Non-ganglionic lesions include solid organ lesions (eg, liver, spleen, kidneys, lungs), gastrointestinal involvement, skin lesions, or those seen on palpation. Unmeasured lesions: Any disease not selected as a measure, dominant disease, and truly evaluable disease should be considered unmeasured. These sites include all nodes, lymph node masses, and extranodal sites that were not selected as dominant or measurable or that do not meet the measurability requirements but are still considered abnormal, as well as truly evaluable disease, which is any site of suspected disease that may be difficult to follow quantitatively with measurement, including pleural effusions, ascites, bone lesions, leptomeningeal disease, abdominal masses, and other lesions that cannot be confirmed and followed by imaging. In Waldeyer's ring or at extranodal sites (eg, gastrointestinal tract, liver, bone marrow), FDG uptake may be greater than in the mediastinum with a complete metabolic response, but should not be greater than normal physiologic uptake. Surrounding (e.g., with spinal activation as a result of chemotherapy or myeloid growth factors).

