## 4.2 EXCLUSION CRITERIA

1. Aggressive histological variants: blastic and pleomorphic variants (blastoid).
2. Proliferation index measured by Ki-67 > 30%.
3. B-cell monoclonal lymphocytosis with MCL phenotype.
4. Eastern Cooperative Oncology Group (ECOG) performance status  $\geq 2$ .
5. Presence of B symptoms or any relevant symptoms related to the MCL.
6. Nodal clinical forms with lymph node enlargement > 3 cm (maximum diameter).
7. Cytopenias attributable to MCL: Neutrophil count <  $1 \times 10^9/L$ , Hemoglobin level < 100 g/L or platelet count <  $100 \times 10^9/L$ .
8. Organ dysfunction related to MCL including creatinine level > 2 ULN or altered liver biochemistry (> 3x ULN).
9. Gradual increase in different determinations of serum LDH attributable to MCL that exceeds 20% of the ULN.
10. Known CNS infiltration.
11. Subjects with expected therapy requirement for MCL in a short time (< 3 months).
12. Patients with active hepatitis B or C infection or HIV infection. Positive test results for chronic HBV infection (defined as positive HBsAg serology) or positive test results for hepatitis C (hepatitis C virus [HCV] antibody serology testing) will be excluded with the following exceptions. Patients with occult or prior HBV infection (defined as negative HBsAg and positive total HBcAb) may be included if HBV DNA is undetectable, provided that they are willing to undergo monthly DNA testing or antiviral prophylaxis. Patients who have protective titers of hepatitis B surface antibody (HBsAb) after vaccination or prior but cured hepatitis B are eligible. Patients positive for HCV antibody are eligible only if PCR is negative for HCV RNA.
13. Anticoagulation requirement with vitamin K antagonists.
14. Past medical history of stroke or intracranial haemorrhage within 6 months prior to inclusion.
15. Required medication with strong CYP3A4/5 inhibitors.
16. Any serious comorbidity that makes the patient unacceptable for receiving the treatment
17. Concomitant or previous malignancies the last 2 years other than basal skin cancer or in situ uterine cervix cancer.
18. Pregnancy or lactation.
19. Major surgery within 4 weeks of inclusion.
20. Clinically significant cardiovascular disease such as uncontrolled or symptomatic arrhythmias, congestive heart failure, or myocardial infarction within 6 months of Screening, or any Class 3 (moderate) or Class 4 (severe) cardiac disease as defined by the New York Heart Association Functional Classification.

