### 5.3.1 Response definitions

The response obtained will be classified according to the 2014 criteria of Cheson et al. (13) (see Annex VII). The PET / CT will be reviewed by GELTAMO PET platform.

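### Annex VII words the nodal part of CT-based complete response as a cap on shrinkage, not as a residual size, and the stage 1 stopping rule depends on CT

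*Protocol*

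**What the plan says.** Section 5.3.1 makes Annex VII the working definition of response: "The response obtained will be classified according to the 2014 criteria", with a pointer to the annex. The annex has a PET-CT column and a CT column.

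In the CT column, the nodal line for complete response reads "Target ganglia / ganglion masses should decrease by $\leq 1.5$ cm in LDi". The abbreviations define the measure as a size: "LDi, longest transverse diameter of a lesion".

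The neighbouring CT rows read as follows:

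- Partial response needs at least a 50% "decrease in SPD of up to 6 measurable target nodes and extranodal sites".
- Stable disease is "<50% decrease from baseline in SPD of up to 6 dominant measurable nodes and extranodal sites", without progression.
- Progression in an existing node requires it to be "abnormal with: LDi > 1.5 cm and ≥50% increase from PPD nadir".
- A new node counts as progression as "A new node > 1.5 cm on any axis".

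Section 7 evaluates complete response at 6 months with thoracoabdominopelvic CT and bone marrow aspirate, with no PET. The trial ends if 5 or fewer of the first 15 patients have a complete response. Section 5.1 assesses the 12-month primary endpoint by PET-CT and marrow biopsy.

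**The concern.** The word *by* turns a limit on residual size into a limit on the amount of change. Taken literally, the criterion runs backwards: a node that barely shrinks satisfies it, and one that disappears from 3 cm does not. No other section states the CT nodal rule, so the protocol offers no correct version to fall back on.

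What is at stake is the stage 1 decision. The 6-month evaluation uses CT without PET, so the CT column is the one that applies. Section 3.3 promises central review of response by imaging in general terms, but sections 5.3.1 and 5.5 specify that review for PET and PET/CT. The protocol therefore does not clearly send the 6-month CT to readers who would catch the slip.

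**Working it through.** The protocol gives no figure to reproduce here. The check applies two readings of the same cell and compares each with the annex's other rows.

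**Inputs.** Exclusion criterion 6 (section 4.2) rules out nodal forms with nodes above 3 cm, so baseline LDi is at most 3.0 cm. The 1.5 cm and 50% limits are from Annex VII. The stage 1 limit is from section 7.

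**Readings.** With baseline b and follow-up f in cm:

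- Literal: 0 < b − f ≤ 1.5.
- Size threshold: f ≤ 1.5.

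To compare with the partial-response and stable-disease rows, assume one round target node (long and short diameters equal). The fall in SPD is then 1 − (f/b)².

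| b → f (cm) | Decrease (cm) | SPD fall | Literal nodal CR | Size-threshold nodal CR |
|---|---|---|---|---|
| 3.0 → 2.8 | 0.2 | 1 − (2.8/3.0)² = 13% | met | not met |
| 2.0 → 1.9 | 0.1 | 10% | met | not met |
| 3.0 → 1.5 | 1.5 | 75% | met | met |
| 3.0 → 1.0 | 2.0 | 1 − (1.0/3.0)² = 89% | not met | met |
| 2.5 → 0.5 | 2.0 | 96% | not met | met |
| 3.0 → 0 | 3.0 | 100% | not met | met |
| 1.6 → 0 | 1.6 | 100% | not met | met |

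The first two rows meet the literal nodal criterion while falling in the annex's stable-disease range (below 50%). The last four fail it with falls of 89% or more.

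**How far the readings differ.** Take b from 1.6 to 3.0 cm in 0.1 cm steps with every smaller f, which gives 16 + 17 + … + 30 = 345 pairs.

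- Literal met, node still above 1.5 cm: 0 + 1 + … + 14 = 105 pairs.
- Literal not met, node at or below 1.5 cm: 1 + 2 + … + 15 = 120 pairs.
- Total disagreement: 105 + 120 = 225 of 345.
- Literal met with an SPD fall below 50% (round node): 93 pairs.

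These are hypothetical size combinations, not patients, so 225/345 is not an expected misclassification rate.

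**Sensitivity of the stage 1 decision.** One reclassified patient changes the outcome only if the correct count is 5 (wrongly raised to 6) or 6 (wrongly lowered to 5). The binomial probability of a count of 5 or 6 in 15 is:

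- at a true rate of 30%: 3003 × 0.3⁵ × 0.7¹⁰ + 5005 × 0.3⁶ × 0.7⁹ = 0.206 + 0.147 = 0.353;
- at 50%: (3003 + 5005)/32768 = 0.244.

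This is the chance of standing next to the boundary, not the chance of an error.

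**The case against.** The strongest reply is that this is a translation slip that no lymphoma reader would follow. The annex is headed as the Lugano criteria, section 5.3.1 cites the 2014 source, other wording in the document is visibly translated, and a rule that denies complete response to a vanished node is absurd on its face. That is a fair account of the likely cause. It does not make the text correct, and the protocol cannot show which rule readers applied.

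Several stronger inferences are tempting, and the documents do not support them.

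- *Almost no shrinkage gives a complete response, or complete response is easier than partial.* Not at patient level. CT-based complete response also requires no extralymphatic disease, no non-measured lesions, normal organ size, no new lesions and normal marrow. Inclusion criterion 7 admits non-nodal disease, mainly in marrow or blood, where the nodal line may not matter at all.
- *The primary endpoint is compromised.* Section 7 does attach the label of primary analysis to the 6-month evaluation, but the endpoint defined in section 5.1 is at 12 months and uses the PET-CT column.
- *All later CT assessments are affected.* PFS and the end of response duration depend on progression, death or new treatment, and the progression rows use 1.5 cm as a size. ORR is fixed at 12 months. No listed endpoint is a CT-based complete response rate after that.
- *Stage 1 was decided on this wording.* The revision sheet says version 3.2 (September 2020) updated the annexes, and the synopsis puts the end of recruitment at December 2019. The annex in force at the stage 1 decision is not visible.
- *A new lesion would not prevent partial response.* The CT partial-response entries for organ enlargement and new lesions look shifted, but this may come from reading the table out of PDF. A new lesion meeting the progression rows counts as progression in any case.

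**Conclusion.** The cell is wrong as written and contradicts the rows around it. Applied literally, it would misclassify the nodal component of CT response in both directions. Its main consequence is for the 6-month count in section 7, where one patient can decide between 5 and 6 complete responses.

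The actual effect cannot be sized: the protocol does not say how many of the first 15 patients had target nodes, and there is no evidence of a literal read.

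The conclusion rests on the annex's own internal use of 1.5 cm as a size, not on the cited source. The round-node assumption affects only the SPD percentages and the count of 93; the contradiction does not depend on it.

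**What to change.** Reword the cell so that target nodes and nodal masses must regress **to** 1.5 cm or less in LDi, in line with the rest of the annex, and verify it against reference 13. At the same time, compare the CT partial-response rows for organ enlargement and new lesions with the source table; no change is needed there if the shift is only in the extracted text.

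Confirm and record that the 6-month stage 1 CT reads used the size threshold, including which annex version was in force. If any did not, re-read those scans and restate the stage 1 count.

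The cost is a one-cell correction and a check of at most 15 patients' 6-month scans, limited to those with target nodes. Sample size, visits and endpoints do not change.
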